**NCT03504943**

## **Timing of intradialytic exercise and its impact on intradialytic hypotension: a randomized crossover study**

[name] [name]; [name] BSc(Hon); [name] [name]; [name] [name]

Intradialytic hypotension (IDH) is a common complication during hemodialysis, occurring in 20-30% of HD treatments. The Kidney Disease Outcomes Quality Initiative defines IDH as a decrease in systolic blood pressure by  $\geq 20$  mmHg or a decrease in Mean Arterial Pressure by  $\geq 10$  mmHg associated with the following symptoms: abdominal discomfort, yawning, sighing, nausea, vomiting, muscle cramps, restlessness, dizziness or fainting, and anxiety. IDH is caused by factors that reduce cardiac output and peripheral resistance, including high ultrafiltration rate, arterial stiffness, abnormal baroreflex sensitivity, ineffective vasoregulation and left ventricular hypertrophy.

Intradialytic hypotension can cause unpleasant symptoms for HD patients including dizziness, cramps and nausea, which lead to interruption of HD and inadequate dialysis. IDH can also lead to decline in residual kidney function, vascular access thrombosis, ischemic damage to white matter of the brain, volume overload, increased risk of cardiovascular events and increased mortality risk. Research conducted by Iseki et al. on HD-associated hypotension showed an inverse correlation between death rate and diastolic blood pressure. Shoji et al. looked further into HD-associated hypotension and discovered that there was an increased two-year mortality risk in HD patients who experienced IDH.

Intradialytic exercise has been shown to improve physical function and health-related quality of life and may ameliorate several dialysis-related symptoms. In addition, studies have demonstrated improved cardiac function, including increased left ventricular ejection fraction and decreased systolic pulmonary artery pressure and right ventricle size with intradialytic exercise. Initial concerns regarding the potential for intradialytic exercise to increase the rate of IDH have been mitigated by multiple interventional studies in which intradialytic exercise has been shown to be safe with minimal adverse effects. In addition, Leung et al demonstrated no increased IDH with intradialytic cycling when exercise was performed in the first half of HD as compared to no exercise. However, concerns regarding the potential of intradialytic exercise to increase frequency of IDH if exercise is performed in second half of HD remain. This is due to the potential risk of exacerbating intradialytic hypotension with post-exercise reductions in blood pressure in the latter half of dialysis when blood pressure (BP) and cardiac output may be lowest. This potential risk has not been rigorously studied prospectively and increased cardiac output and venous return associated with exercise may mitigate the effects of post-exercise hypotension in this setting. Farese et al. observed a significant (11 mmHg) increase in overall dialysis treatment systolic blood pressure with 3 weeks of passive cycling movement during HD (as compared to a non-intervention dialysis treatment), but the study did not comment on timing of intradialytic exercise. Rhee et al. found that decreases in systolic blood pressure improved as

exercise, completed in first half of dialysis, progressed over a 6-month period. In addition to improvement in systolic blood pressure, a significant reduction ( $p < 0.05$ ) in IDH episodes was observed. Conversely, in a cross-sectional study conducted by Dungey et al, exercise that commenced 60 minutes after dialysis start significantly increased systolic blood pressure immediately post-exercise but SBP significantly decreased (106 vs. 117 mmHg;  $p < 0.001$ ) 1 hour post exercise as compared to no exercise. Many previous studies investigating the effects of intradialytic exercise have limited exercise sessions to the first half of HD due to concerns of potentiating IDH if exercise is performed in the latter half of an HD session. Anecdotally, a number of individuals in our clinical intradialytic cycling program have cycled during the last half of HD with no ill effects. The ability to safely perform intradialytic exercise in the second half of HD would allow more flexibility in exercise timing and facilitate availability of exercise equipment and staff to help with exercise by potentially avoiding exercise at the beginning of HD (often the busiest time with the most nursing tasks). Timing of exercise later in HD treatment may also decrease frequency of cramping and restless legs symptoms, which have a propensity to occur in the latter part of HD sessions.

No study has specifically compared the frequency IDH episodes when exercise is performed during second half of HD as compared to that when exercise is performed during the first half of a HD session to fully characterize the effect of timing of intradialytic exercise and its effect on IDH.

We aim to address this knowledge gap with a randomized crossover study examining the rate of IDH when individuals in a clinical intradialytic cycling program exercise during the first half of their hemodialysis session as compared with the IDH rate when exercise is performed during the second half of hemodialysis.

## **METHODS**

**Research Question:** In individuals on maintenance HD, does cycling exercise performed during the second half of HD result in a higher rate of intradialytic hypotension than exercise performed in the first half of HD?

### **Objectives:**

1. To compare the rate of IDH when intradialytic exercise is performed in the first half of the HD session as compared with that when intradialytic exercise is performed in the second half of HD.
2. To compare the prevalence of hemodialysis related symptoms when intradialytic exercise is performed in the first half of the HD session as compared with symptom prevalence when exercise is performed in the second half of HD.

3. To compare recovery time post HD when intradialytic exercise is performed in the first half of the HD session as compared with recovery time post HD when exercise is performed in the second half of HD.

**Study Design:** Multi-centre randomized crossover study comparing the rate of IDH over a 2-week period in 90 individuals on chronic HD when intradialytic cycling is performed in the first half of HD as compared with the rate of IDH when intradialytic cycling is performed in the second half of HD for 2 weeks.

**Population/Setting:** Adults with end-stage renal disease on chronic (>3 months) in-centre HD who are already participating in the Northern Alberta Renal Program (University of Alberta Hospital, Grey Nuns Hospital, Edmonton General Hospital, and St. Paul's Dialysis Unit); Southern Alberta Renal Program (Sheldon Chumir Hemodialysis Unit, South Calgary Hemodialysis Unit, Peter Lougheed Centre, North East Dialysis Centre, Northland Dialysis Centre); or the Manitoba Renal Program (Sherbrook Centre Dialysis Unit, Central Dialysis Unit and Seven Oaks Hemodialysis Unit) clinical intradialytic cycling programs are eligible to participate. Participants will act as their own comparisons.

*Inclusion criteria:* adult ( $\geq 18$  years old); receiving three times per week intermittent hemodialysis sessions; able to communicate in English; able to provide informed consent

*Exclusion criteria:* dialysis frequency not three times per week

**Recruitment, Enrolment and Assessments:**

Individuals receiving HD at SCDU and SOGH who are currently participating in the Manitoba Renal Program's clinical intradialytic cycling program (see below) will be contacted by dialysis unit staff regarding their interest in being approached to participate in this study. If agreeable to initial approach, study staff will visit patients during their usual HD session, provide information about the study and obtain written consent. We plan to recruit a total of 30 patients from Winnipeg. These patients will act as their own comparisons. All recruited patients are already cycling during their regularly scheduled HD sessions as part of the MRP clinical intradialytic cycling program. No new intervention will be applied as part of this study. Participants will simply change the timing of their intradialytic cycling for 2 out of the 4 weeks of the study. Participants will be randomly assigned (computer generated randomization list generated by a third party) to study Group 1 or Group 2 with even distribution between each group. Similar recruitment procedures will occur in Calgary and Edmonton.

**Withdrawal of subjects:**

Patients may withdraw from the study at any time with or without giving a reason. If the reason is given, it will be recorded on the case report form and primary investigator will be notified of withdrawal.

**Intervention:**

To facilitate study implementation and optimize use of exercise resources and equipment, participants at each site will be randomly split into 2 groups. Group 1 will perform 2 weeks of their usual intradialytic cycling (6 sessions) during the first half of their usual HD and then perform 2 weeks of intradialytic cycling (6 sessions) during the second half of their usual HD. Group 2 will perform the intervention in reverse order to Group 1 (See Figure 1). No washout period is required as there is no biological plausibility for carry over effect. However, as participation in the cycling program is voluntary, some participants may choose not to exercise during some of their HD sessions. We will monitor these non-cycling sessions for IDH as well and will compare IDH rate in these non-exercise sessions with IDH rate during sessions when intradialytic exercise was performed.

Participants will perform their usual duration and intensity of intradialytic cycling at each HD session as per clinical intradialytic cycling protocol procedures (see below). Prescribed exercise time and intensity will remain unchanged over the course of the study.

We will attempt to keep dialysate composition, dialyzer, dialysate temperature, HD access, dialysis duration and medications unchanged over the course of the study, but will not intervene/interfere with usual clinical care. The research assistant will record any changes to dialysis prescription related to routine clinical care on a weekly basis.

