**Manitoba Renal Program's Clinical Intradialytic Cycling Program:**

In this pre-existing clinical program, individuals cycle on a stationary ergometer during their regular HD sessions while supervised by a kinesiologist. At present, 60 individuals are participating in this program at SCUDU and SOGH. Participants cycle in the first half of each HD session (usually 30-60 minutes) on TherapyCycle™ (Greely, CO) ergometers modified for dialysis chairs with a target exercise intensity of 3-4/10 on the Borg Rating of Perceived Exertion (RPE), which is considered to be moderate intensity. Rest periods are provided as needed if participants are unable to complete their target duration of continuous exercise. Duration of total exercise time and self-reported exercise intensity (Borg RPE) is recorded by participants/kinesiologist for each exercise session. The study kinesiologist adjusts cycling duration and ergometer resistance in consultation with each individual patient. HD unit staff assist with set up and monitoring of exercise sessions. In addition to routine HD monitoring (blood pressure and pulse before, after and every 30 min during HD and glucose pre and post HD in diabetics) participants have blood pressure, pulse and glucose (in individuals with diabetes) measured before and after completion of each intradialytic exercise session. The program is voluntary and participants choose not to cycle during some HD sessions. Program participants have physical function (4 metre gait speed, grip strength, shuttle walk test), health-related quality of life (EQ5D-3L) and self-reported physical activity level (Godin Leisure Time Exercise Questionnaire) measured prior to participating in the intradialytic program and every 6 months thereafter while enrolled in the exercise program.

Calgary and Edmonton have similar clinical intradialytic cycling programs from which

participants will be enrolled. Those 2 sites will receive ethics approval for their site through their respective University ethics boards.

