**BP Measurement:**

We will use the initial BP measurement obtained once the patient has commenced HD (i.e. patient “hooked up” and blood present in both venous and arterial lines) for the *baseline BP*. Blood pressure will be measured as per routine procedures used in the participants’ HD units (usual arm/leg, usual BP cuff). Pre and post HD BP will be collected as per usual HD Unit practice. During HD, BP will be collected more frequently than the usual HD routine (q30 min) at q15min intervals or more frequently when clinically indicated based on patient symptoms or status. This timing will be pre-programmed into HD machines to minimize work for bedside HD nurses. However, bedside HD nurses will need to record each BP measurement on the HD run sheet. Research assistant and/or clinical exercise program kinesiologist will be present at each cycling session to ensure outcome data is being collected.

**Primary Outcome:** *Difference in rate of intradialytic hypotension* between the 2 study time periods (early and late intradialytic exercise). Rate of IDH will be reported as episodes of intradialytic hypotension per 100 hours of HD. Intradialytic hypotension will be defined as the composite of >20 mmHg drop from baseline BP OR a drop in systolic BP to <90 mmHg during HD. A >20 mmHg reduction in blood pressure is justified as this magnitude of reduction from baseline BP has been associated with occurrence of HD-induced cardiac injury. In addition, a nadir BP of <90mmHg is the only definition of IDH associated with increased risk of mortality.

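### Exercise duration in the primary timing model, and a cycled versus non-cycled comparison with no time window, both let the participant's choice to ride enter the result (minor)

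*Protocol*

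**What the plan says.** - **How a session becomes non-cycled.** In the description of the Manitoba cycling program: "The program is voluntary and participants choose not to cycle during some HD sessions". The Intervention section repeats this for the trial and adds that the investigators "will compare IDH rate in these non-exercise sessions with IDH rate during sessions when intradialytic exercise was performed".
- **What counts as IDH.** The Primary Outcome paragraph (under BP Measurement) defines it as the "composite of >20 mmHg drop from baseline BP OR a drop in systolic BP to <90 mmHg during HD", per 100 hours of HD. Baseline is the first reading on dialysis. The symptomatic definition under Secondary Outcomes is not tied to the ride either.
- **What the primary contrast is.** The Primary Outcome paragraph takes the difference in rate "between the 2 study time periods (early and late intradialytic exercise"). Objective 1 is worded by performance: "To compare the rate of IDH when intradialytic exercise is performed in the first half of the HD session", set against the second half.
- **The model.** The Data analysis section specifies linear mixed models for timing of exercise and IDH, accounting for duration of exercise, UF rate and within-patient data.
- **Duration.** Under Intervention: "Prescribed exercise time and intensity will remain unchanged over the course of the study". In the program description: "Duration of total exercise time and self-reported exercise intensity (Borg RPE) is recorded" for each exercise session.
- **Reference values.** Sample Size Estimation gives 130 episodes per 100 h and treats a 20% increase with late exercise as unacceptable.

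**The concern.** Two choices stated in the protocol let something that happens after randomisation shape a comparison.

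First, duration in the primary model. Prescribed time is held constant and actual time is recorded, so on the natural reading the covariate is actual time. Within a patient it then varies only through rides that are skipped, cut short or adjusted by the kinesiologist. If hypotension before or during a late ride causes any of these, the model adjusts for a consequence of the outcome.

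Second, the non-cycled versus cycled comparison. A late ride falls in the second half of HD, so first-half readings precede the decision to ride. If a ride is declined after early hypotension, that hypotension is counted in the non-cycled session. The outcome then determines the exposure group.

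Readings may also differ between the two kinds of session. Cycled sessions gain readings before and after the ride, and any session gains readings "more frequently when clinically indicated based on patient symptoms or status". The net direction of this is unknown.

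The trial asks whether late exercise is less safe. If the assumed mechanism operates, duration adjustment favours late exercise and the session comparison favours cycling.

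**Working it through.** **Inputs from the protocol.** IDH rate 130 per 100 h; unacceptable increase 20%, so 0.20 × 130 = 26 per 100 h; readings every 15 min; 6 early and 6 late sessions per participant.

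**Assumptions, not in the documents.** 4-h sessions (16 readings); every qualifying reading counted; 40% of them in the first half; 15% of rides skipped for unrelated reasons; patient and session effects normal with logit SD 0.7 each. In addition, a share s of late rides is skipped when at least 2 qualifying readings precede the ride. Exercise and its timing have no true effect. Expected qualifying readings per session: 130 × 4/100 = 5.2, of which 0.40 × 5.2 = 2.08 fall in the first half.

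**1. Duration as covariate** (skipped = 0, prescribed = 45 min). In a linear model

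adjusted late effect = unadjusted late effect − b × (mean rides per late session − mean rides per early session),

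where b is the within-patient coefficient per 45-min ride. By assigned timing the unadjusted late/early ratio is 1.00. The simulated b is spurious, −9 to −14 per 100 h at s = 20-30%. The late effect becomes −0.8% at s = 20% and −1.5% at s = 30%. Check at 30%: −1.5% × 130 = −1.95 per 100 h, and 1.95/14 = 0.14 fewer rides per late session, so 0 − (−14) × (−0.14) ≈ −1.96. If 20-30% of rides with hypotension during the ride are also cut short, the shift reaches −2.9%.

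A second model (Poisson episodes, 10% background skipping) gives −0.7 and −2.2 per 100 h at 130 per 100 h when 30% or 50% of late rides are skipped after first-half IDH: −0.7/130 = −0.5% and −2.2/130 = −1.7%. Only a far more extreme pair of inputs leaves the 0-3% range clearly, for example 50% skipping at 20 per 100 h: −1.2/20 = −6%.

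**2. Non-cycled versus cycled sessions** (ratios from unrounded rates):

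| s | Non-cycled, per 100 h | Cycled, per 100 h | Ratio |
|---|---|---|---|
| 10% | 137 | 129 | 1.07 |
| 20% | 142 | 127 | 1.12 |
| 30% | 147 | 125 | 1.17 |

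- One reading as trigger: 1.04, 1.07, 1.10.
- s = 20%, varying first-half share (30-50%), logit SD (0.5-1.5) and ride start (0-60 min after the midpoint): 1.04-1.17.
- s = 20%, background skipping 5% or 30%: 1.24 or 1.08.
- Consecutive qualifying readings merged into one episode (26-61 per 100 h): 1.10-1.22.
- Poisson model at 130 per 100 h, 30% or 50% skipping: 1.05 or 1.07. At 50 and 20 per 100 h with 30% skipping it gives 1.17 and 1.33, so the ratio grows when episodes are rarer.
- Skipping unrelated to IDH: about 1.00.

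**3. Which counting window works** (s = 20-30%, rides starting 30-60 min after the midpoint, stratified by earlier readings). Counting from the HD midpoint leaves 1.02-1.04, or 1.05-1.08 if skipping follows a reading between midpoint and ride start. Counting from the planned start returns about 1.00, provided skipping depends only on recorded readings before it. If IDH-prone patients skip more, 1.06-1.11 remains without, and 1.00 with, a within-patient comparison. If skipping follows an unrecorded state of that session, 1.06-1.13 remains even within patient.

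**4. Dilution in the all-session analysis.** Suppose a true 20% increase is confined to cycled late sessions. With 15% unrelated skipping it reads as 0.85 × 20% = 17%. Adding dependent skipping at s = 20% and 30%, the simulation gives 14% and 13%. The within-patient cycled-only figures are 20%, 16% and 13-14%.

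**The case against.** The strongest case against has four parts.

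- **The mechanism is assumed.** The protocol gives voluntary choice as the only source of skipping. This stands: the size is unknown and the ratios above move with the assumed skipping.
- **Duration could mean prescribed time.** The Data analysis section does not say which. If prescribed, it is constant within a patient and harmless to this contrast. This stands as a possible reading, but actual time is what the protocol says is recorded, and the wording should settle it.
- **The session comparison is ancillary and its details belong in an SAP.** It is not a listed objective or outcome, which is one reason the point is minor. But the protocol itself commits to the comparison and to outcome definitions without a ride-related window.
- **The remedy pulls toward no difference too.** It does: by step 4, the all-session analysis understates a true increase about as much as a cycled-only one, or more. Its advantage is that it keeps the randomised comparison and is unbiased when there is no effect.

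A reader might go further and infer from Objective 1 that the primary analysis uses cycled sessions only. Late/early would then fall by about 1-7% in a within-patient model under the same assumptions. The protocol does not state such an analysis: its Primary Outcome compares the two periods, which implies keeping all sessions. Nor do the documents support reading any simulated percentage as the bias to expect in this trial.

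**Conclusion.** The point holds as a minor one. On the natural reading, the primary model adjusts for a variable that arises after randomisation and that skipping or shortening a ride changes. If hypotension drives some of that, the late effect moves in favour of late exercise by roughly 0-3%, for dependent skipping up to 30% at the protocol's rate. That is small against 20%. The non-cycled versus cycled comparison is open to reverse causation that could make cycling look protective. Illustrative ratios under no effect are about 1.04-1.25 at or near the protocol's conditions. Both figures rest on assumed skipping behaviour. They show direction and order of size, and do not show that the trial's conclusion would change.

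**What to change.** **Data analysis section.** State that the primary contrast uses all attended HD sessions by the timing assigned for that period, without actual exercise duration in the model. Report cycled-only and duration-adjusted results as supportive, with the number of skipped rides per period. Because of the dilution in step 4, show the cycled-only result directly beside the primary one.

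**Intervention section.** Label the non-cycled versus cycled comparison non-randomised and exploratory, and make it within patient. Count only episodes after the planned ride start, from the scheduled 15-minute readings, adjusting for episodes before that time. State that bias from unrecorded symptoms remains.

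**Cost.** Wording in two sections and one data item. Neither the program description nor Data Collection and Management lists a ride start time, so a planned start per patient and period (two entries) would be recorded in advance. It serves only as a reference time for the analysis and exists for skipped sessions too. The 15-minute readings are already planned. The restricted comparison uses fewer episodes and is less precise.

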**Manitoba Renal Program's Clinical Intradialytic Cycling Program:**

In this pre-existing clinical program, individuals cycle on a stationary ergometer during their regular HD sessions while supervised by a kinesiologist. At present, 60 individuals are participating in this program at SCUDU and SOGH. Participants cycle in the first half of each HD session (usually 30-60 minutes) on TherapyCycle™ (Greely, CO) ergometers modified for dialysis chairs with a target exercise intensity of 3-4/10 on the Borg Rating of Perceived Exertion (RPE), which is considered to be moderate intensity. Rest periods are provided as needed if participants are unable to complete their target duration of continuous exercise. Duration of total exercise time and self-reported exercise intensity (Borg RPE) is recorded by participants/kinesiologist for each exercise session. The study kinesiologist adjusts cycling duration and ergometer resistance in consultation with each individual patient. HD unit staff assist with set up and monitoring of exercise sessions. In addition to routine HD monitoring (blood pressure and pulse before, after and every 30 min during HD and glucose pre and post HD in diabetics) participants have blood pressure, pulse and glucose (in individuals with diabetes) measured before and after completion of each intradialytic exercise session. The program is voluntary and participants choose not to cycle during some HD sessions. Program participants have physical function (4 metre gait speed, grip strength, shuttle walk test), health-related quality of life (EQ5D-3L) and self-reported physical activity level (Godin Leisure Time Exercise Questionnaire) measured prior to participating in the intradialytic program and every 6 months thereafter while enrolled in the exercise program.

Calgary and Edmonton have similar clinical intradialytic cycling programs from which

participants will be enrolled. Those 2 sites will receive ethics approval for their site through their respective University ethics boards.

